7.3. Assessment of Adverse Events

All AEs will be assessed by the investigator and recorded in the case report form, including the dates of onset and resolution, severity, relationship to Study drug, outcome, and action taken with Study medication.

7.3.1. Severity

The term “severe” is often used to describe the intensity (severity) of a specific event (as in mild, moderate, or severe myocardial infarction); the event itself, however, may be of relatively minor medical significance (such as severe nausea). This is not the same as “serious,” which is based on patient/event outcome or action criteria usually associated with events that pose a threat to a subject’s life or functioning. The severity of AEs will be assessed according to the following definitions:

- **Mild:** the AE is noticeable to the patient and/or the Investigator but does not interfere with routine activity.
- **Moderate:** the AE interferes with routine activity but responds to symptomatic therapy or rest.
- **Severe:** the AE significantly limits the patient’s ability to perform routine activities despite symptomatic therapy.

7.3.2. Causal Relationship to Study Medication

The Investigator’s assessment of causality is based on clinical judgment regarding the reasonable possibility that the Study medication caused the event and may include consideration of some or all of the following factors:

- Possible alternative causes of the AE, including the disease under treatment, co-morbid conditions, other drugs, and environmental factors.
- The temporal association between drug exposure and onset of the AE.
- Whether the clinical or laboratory manifestations of the AE are consistent with known actions or toxicity of the Study medication.
- Whether the AE resolved or improved with decreasing the dose or stopping the Study medication (“dechallenge”) or recurred or worsened upon re-exposure to the Study medication (“rechallenge”).

The causal relationship between the Study medication and the AE will be described using one of the following categories:

- **Not Related:** Evidence exists that the adverse event has an etiology other than the Study drug (such as a preexisting condition, underlying disease, intercurrent illness, or concomitant medication).
- **Related:** A temporal relationship exists between the event onset and administration of the Study drug. It cannot be readily explained by the subject’s clinical state or concomitant

therapies and appears with some degree of certainty to be related based on the known therapeutic and pharmacologic actions of the drug. In case of cessation or reduction of the dose, the event abates or resolves and reappears upon rechallenge. It should be emphasized that ineffective treatment should not be considered as causally related in the context of adverse event reporting.

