6.6. Discontinuation

6.6.1. Subject Discontinuation

Any subject may withdraw their consent to participate in the Study at any time without prejudice. The investigator must withdraw from the Study any subject who requests to be withdrawn. A subject's participation in the Study may be discontinued at any time at the discretion of the investigator and in accordance with his or her clinical judgment. Subjects must also be discontinued on study drug for any AESI (except non-melanoma skin cancer, mono-dermatomal

herpes zoster, and certain laboratory abnormalities that are deemed by the investigator to not place subjects at immediate safety risk) or if the subject becomes pregnant. When possible, the tests and evaluations listed for the termination visit should be carried out. If a subject withdraws before completing the Study, the reason for withdrawal is to be documented on the CRF.

The Sponsor will be notified of all subject withdrawals.

Reasons for which the investigator or the Sponsor may withdraw a subject from the Phase 2b/Phase 3 Induction Studies or Phase 3 Maintenance Study or a subject may choose to terminate participation before completion include the following:

- Adverse event
- Subject choice/Withdrawal of consent
- Major violation of the protocol
- Termination of the Study by the Sponsor
- Initiation of a prohibited medication ([Appendix 6](#)) for UC (except for rectal aminosalicylates and rectal corticosteroids during the clinical flare assessment)
- Lost to follow-up
- Pregnancy
- Colectomy

Subjects with laboratory abnormalities as outlined in Section 7.2 (i.e., two sequential occurrences of renal, leukocyte, leukocyte subset, or hepatic panel abnormalities or hepatic panel abnormalities with clinical sign or symptom of acute liver failure) should discontinue the study drug. Any non-laboratory-related AE considered an AESI defined in Section 7.1.4, except for non-melanoma skin cancer and mono-dermatomal herpes zoster, should also lead to study drug discontinuation. Subjects who discontinue Study drug early because of an adverse reaction should be encouraged to continue their participation in the follow-up safety assessments. If a subject fails to return for scheduled visits, a documented effort must be made to determine the reason.

Subject study completion is defined as completing the last study visit whether or not the subject discontinued study drug prematurely.

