7.1.4. Adverse Events of Special Interest (AESI)

At each Study visit, the Investigator (or designee) will specifically query for any adverse events of special interest (AESI). The following events are considered AESIs for this Study:

- Suspected or confirmed intestinal perforation
- Complicated herpes zoster (multi-dermatomal, disseminated, or with ophthalmic or CNS involvement)
- Malignancy excluding non-melanoma skin cancer
- Non-melanoma skin cancer
- Serious infection (e.g., that requires hospitalization or intravenous antibiotics)
- Opportunistic infections
- Thromboembolic disease (e.g., DVT, pulmonary embolism)
- Clinical laboratory abnormalities of concern (Refer to Section 7.2)
- Major cardiovascular event (e.g., myocardial infarction or cerebrovascular accident)

All AESIs, except for non-melanoma skin cancers and mono-dermatomal herpes zoster, must be reported to TBPH Clinical Safety and Pharmacovigilance within 24 hours of the time the Investigator or his/her designee becomes aware of an AESI (Refer to Section 7.4.3). Except for non-melanoma skin cancer that has been fully resected, mono-dermatomal herpes zoster, and certain laboratory abnormalities that are deemed by the investigator to not place subjects at immediate safety risk, all of these AESI’s should lead to discontinuation of the study drug. For each of these AESI, an additional targeted questionnaire needs to be completed to assess for risk factors. For thromboembolic events in particular, the subject should undergo evaluation for hypercoagulable state (e.g., with clinically relevant investigations, such as referral to a specialist and/or blood testing for a predisposition to a hypercoagulable state) and repeat imaging to assess resolution of the finding.

Besides these AESI, for other AEs, study drug may be interrupted and resumed as deemed medically appropriate by the investigator (e.g. during an infection that requires oral antimicrobial treatment).

7.2. Clinical Laboratory Abnormalities and Other Abnormal Assessments as Adverse Events or Serious Adverse Events

Abnormal laboratory findings (such as clinical chemistry, hematology, or urinalysis) or other abnormal assessments (such as electrocardiograms [ECGs], X-rays, or vital signs) that are associated with signs and/or symptoms or are considered clinically significant in the judgment of the investigator must be recorded as AEs or SAEs if they meet the definition of an adverse event

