7.4.3. SAE and AESI Reporting Timeline

SAEs and AESIs will be reported to Clinical Safety and Pharmacovigilance within 24 hours of the time the Investigator or his/her designee becomes aware that a SAE or AESI has occurred, whether or not the event is considered to be related to Study medication. If the initial SAE is reported by telephone, a written report signed by the Investigator must be submitted within 24 hours.

The SAE/AESI Report Form must be completed in accordance with the SAE/AESI Report Form Completion Guidelines. If all information on the SAE/AESI Report Form is not available at the time of the initial report, follow-up SAE/AESI reports will be completed and submitted.

To report an SAE or AESI, complete and fax or email the SAE/AESI Report Form to the following:

Theravance Biopharma Clinical Safety and Pharmacovigilance

[REDACTED]

For medical questions regarding an SAE, contact the Sponsor medical monitor by telephone as follows:

Sponsor Medical Monitor Contact Information:

Telephone: [REDACTED]

For fatal or life-threatening events, also fax copies of hospital case reports, autopsy reports, and other documents when requested. Additional information may be requested from the investigator to ensure the timely completion of accurate safety reports.

An SAE may qualify for reporting to regulatory authorities if the SAE is possibly attributable to the Study drug and is unexpected/unlisted based on the current TD-1473 Investigator's Brochure. In this case, all investigators will receive notification of the event. The investigator is responsible for notifying the Institutional Review Board or Ethics Committee and documenting the notification, as required by local regulatory authorities and in accordance with the local institutional policy.

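### Protocol 7.3.2 sets a reasonable-possibility standard for causality, but its two categories apply other tests, so some events fit neither and drug-related counts are hard to interpret

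*Protocol*

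**What the plan says.** - **Lead-in to Protocol 7.3.2.** The investigator's assessment is "based on clinical judgment regarding the reasonable possibility that the Study medication caused the event". It "may include consideration of some or all of the following factors", one of which is what happened on dechallenge or rechallenge.
- **Categories in 7.3.2.** Each event must then go into one of two. *Related* needs a link in time, no ready explanation from the subject's condition or other treatment, and an event that "appears with some degree of certainty to be related" given the drug's known actions. It continues: "In case of cessation or reduction of the dose, the event abates or resolves and reappears upon rechallenge". *Not Related* reads: "Evidence exists that the adverse event has an etiology other than the Study drug".
- **Stopping text.** Protocol 6.6.1 says: "Subjects must also be discontinued on study drug for any AESI". Protocol 7.1.4 says AESIs "should lead to discontinuation of the study drug". Both list exceptions: non-melanoma skin cancer (in 7.1.4, only if fully resected), mono-dermatomal zoster, and certain laboratory abnormalities. For other AEs, 7.1.4 allows the drug to be interrupted and restarted.
- **Reporting.** Under Protocol 7.4.3, SAEs and AESIs go to the sponsor within 24 hours whatever their relatedness. For onward reporting: "An SAE may qualify for reporting to regulatory authorities if the SAE is possibly attributable to the Study drug", provided it is also unexpected.
- **Outputs.** Protocol 8.8.2 plans tables of drug-related TEAEs and TESAEs. The Phase 2b SAP (3.7.2) plans a drug-related TEAE table. The Maintenance SAP (3.7.2) plans drug-related TEAE and TESAE tables. Both SAPs' overall AE summaries carry lines for related and serious related events.

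**The concern.** The standard announced at the head of 7.3.2 appears in neither category. *Related* is stricter than a reasonable possibility. *Not Related* is not its complement, because it requires positive evidence of something else. An investigator who thinks the drug may well have caused an event, but can show neither recurrence on re-exposure nor another cause, has no category that fits and must still pick one.

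The rechallenge wording sharpens this for AESIs. For most of them the protocol itself orders the cessation that triggers the sentence, and recurrence cannot then be observed without re-exposure.

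At stake is the meaning of the drug-related tables. Two sites that follow the same section in good faith could classify the same AESI in opposite ways.

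**Working it through.** The documents give no figure for related events, so there is nothing to reproduce and no arithmetic to run. The check applies each test in 7.3.2 to the same kinds of event.

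| Type of event | Lead-in: reasonable possibility? | Meets *Related* as written? | Meets *Not Related* as written? |
|---|---|---|---|
| A. Plausible AESI, drug stopped as 6.6.1 and 7.1.4 require, no re-exposure, no proven other cause | Yes | No, on a literal reading: cessation occurred and recurrence was not seen | No: no evidence of another cause |
| B. Plausible event with a ready but unproven alternative explanation | Can be yes | No: a ready explanation exists | No: the alternative is not evidenced |
| C. Plausible non-AESI event, drug interrupted then restarted | Yes | Can be: recurrence is observable | No, unless another cause is shown |
| D. Implausible event with no documented other cause | No | No | No: no evidence of another cause |

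Four things follow.

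1. **There is a gap.** Types A, B and D fit neither category as written. The lead-in would settle A and D, and could settle B.
2. **The gap does not rest on rechallenge alone.** Type B falls through it whichever way the rechallenge sentence is read.
3. **The literal test is harder for AESIs than for other AEs.** Comparing A with C, re-exposure is open under 7.1.4 for ordinary AEs but not for AESIs that require discontinuation.
4. **The direction of any error is not fixed.** Types A and B may be entered as *Not Related*, which lowers the count relative to the lead-in standard. Type D may be entered as *Related*, which raises it. The protocol gives no default.

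On size, let *f* be the share of events like A and B whose assessor sets the lead-in aside, and *g* the share of those then entered as *Not Related*. If all would count as related under the lead-in, the proportional loss for such events is *f* × *g*. The documents give neither value. With both free between 0 and 1, the loss runs from nothing to all of them, which says nothing useful.

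**The case against.** The best reply is that the sentence is conditional and should be read with its lead-in. It describes how a related event behaves if the drug is stopped and given again. Where there is no rechallenge, the limb is untested rather than failed, and clinical judgment still governs. That is a fair reading, and it defeats some inferences that a reader might draw:

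- **That an event is related only if it is fairly certain and recurs, so the gravest events can never qualify.** The certainty wording is milder, rechallenge is an optional factor in the lead-in, and some AESIs are exempt from stopping. The limb is out of reach only on a literal reading of the category.
- **That ambiguous events default to *Not Related*.** Nothing says so, and that category's own demand for evidence works against it.
- **That reporting is biased low.** The 24-hour route ignores relatedness, and regulatory reporting uses a possible-attribution wording. The only reporting expressly tied to relatedness is the optional reporting of SAEs for 30 days after the last visit (7.4.2), although the category chosen could colour the attribution judgment.
- **That related counts fall by about half.** This needs an assumed even split of sites between readings, and every such event related under one and unrelated under the other. No document supports either step.

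It is also true that the main safety tables do not use relatedness and that site assessors are blinded, so misclassification would be expected in all arms. The SAE/AESI form guidelines, which are not provided, may clarify the categories.

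The inconsistency itself remains. The lenient reading is one of two that the text allows, and it does not help type B. Blinding limits bias between arms but does not make the counts consistent or right in level. The blinded events committee (7.3.3) adjudicates thromboembolic and major cardiovascular events and may be asked to take others, but it is not said to assign drug causality.

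**Conclusion.** The point holds as an internal inconsistency in Protocol 7.3.2. The two mandatory categories do not implement the section's stated standard, they leave some events unclassifiable, and on a literal reading one limb of *Related* is out of reach for AESIs that require discontinuation.

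The consequence is confined to outputs that use the category: drug-related TEAE and TESAE counts may be inconsistent between sites and possibly low. Low counts are a plausible risk, not an established result. They depend on investigators applying the category text over the lead-in and then choosing *Not Related*; the documents show neither. All-causality AE, SAE and AESI tables, and 24-hour reporting to the sponsor, stand as planned.

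**What to change.** Define *Related* as a reasonable possibility that study drug caused the event and *Not Related* as no reasonable possibility, with one of the two required for every AE. Remove dechallenge and rechallenge from the category text and leave them in the list of supporting factors, where they already appear. Reconcile the attribution wording in Protocol 7.4.3 and the CRF guidance with this standard. No stopping or rechallenge rule changes.

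The cost is protocol and CRF-guideline wording plus a site memo. The small downside is that more events will be labelled related.

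The Maintenance SAP (section 1) puts all last doses by 11 September 2021 and end-of-study visits by 20 October 2021, so new wording cannot guide assessments already made. Where assessments are complete, the CSR should disclose the inconsistency beside the drug-related tables and rest its safety conclusions on the all-causality tables, which are already planned.

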7.3.3. Clinical Events Committee (CEC)

A clinical events committee (CEC) has been established with external experts and will adjudicate thromboembolic and major cardiovascular events. If deemed necessary, the same or a different CEC may also be requested to adjudicate other AEs of interest (e.g., for opportunistic infections, herpes zoster, malignancy). To allow for unbiased assessment, the CEC will remain blinded to treatment assignment. A CEC charter will be drafted with descriptions of membership, the scope of the CEC members' responsibilities, adjudication processes, and definitions used to review and assess specific AEs.

7.4. AE Reporting and Recording

7.4.1. AE Reporting

Timely, accurate, and complete reporting and analysis of safety information from clinical trials is crucial for the protection of subjects and is mandated by regulatory agencies. Sponsor has established standard operating procedures in compliance with regulatory requirements worldwide to ensure appropriate reporting of safety information. All clinical trials sponsored by TBPH will be conducted in accordance with these procedures.

7.4.2. AE, SAE and AESI Recording

All AEs, regardless of seriousness, severity, or causal relationship to Study medication, will be recorded from signing informed consent through the last Study visit (or last subject contact in the case of a follow-up telephone call). AEs will be recorded on the AE page of the CRF. SAEs, regardless of relationship to Study medication will be recorded from signing informed consent through the last Study visit (or last subject contact in the case of a follow-up telephone call). Additionally, investigators may report SAEs assessed as related to Study medication through 30 days following the last Study visit (or last subject contact in the case of a follow-up telephone call). All SAEs will be recorded on both the SAE Report Form and the AE page of the CRF and should include the following:

Description of event:

- Signs and symptoms due to a common etiology should be reported as a single diagnosis; for example, cough, runny nose, sneezing, sore throat, and head congestion would be reported as “upper respiratory infection”.
- A diagnosis or description must be as specific and as complete as possible (e.g., “lower extremity edema” instead of “edema”).
- Hospitalization or surgical procedures should not be used as adverse event terms (e.g., if a subject was hospitalized for cholecystectomy due to cholecystitis, the

adverse event term should be recorded as cholecystitis, and not as the procedure, cholecystectomy).

- “Death” should not be used as an adverse event term unless the cause of death is unknown. For events with a fatal outcome, the cause of death should be the adverse event term (e.g., if a subject died of an acute myocardial infarction, the adverse event term should be recorded as “Myocardial Infarction” and the event outcome as fatal).
- Relationship to Study medication: The Investigator will make an assessment of the causal relationship of the Study medication to the AE using the guidelines in Section 7.3.2.
- Severity: The severity of the AE will be assessed using the guidelines in Section 7.3.1.
- Outcome: The outcome of AEs will be recorded.
- Therapeutic measures: Measures taken for the treatment or management of the AEs will be recorded.

7.4.3. SAE and AESI Reporting Timeline

SAEs and AESIs will be reported to Clinical Safety and Pharmacovigilance within 24 hours of the time the Investigator or his/her designee becomes aware that a SAE or AESI has occurred, whether or not the event is considered to be related to Study medication. If the initial SAE is reported by telephone, a written report signed by the Investigator must be submitted within 24 hours.

The SAE/AESI Report Form must be completed in accordance with the SAE/AESI Report Form Completion Guidelines. If all information on the SAE/AESI Report Form is not available at the time of the initial report, follow-up SAE/AESI reports will be completed and submitted.

To report an SAE or AESI, complete and fax or email the SAE/AESI Report Form to the following:

Theravance Biopharma Clinical Safety and Pharmacovigilance

[REDACTED]

For medical questions regarding an SAE, contact the Sponsor medical monitor by telephone as follows:

Sponsor Medical Monitor Contact Information:

Telephone: [REDACTED]

For fatal or life-threatening events, also fax copies of hospital case reports, autopsy reports, and other documents when requested. Additional information may be requested from the investigator to ensure the timely completion of accurate safety reports.

An SAE may qualify for reporting to regulatory authorities if the SAE is possibly attributable to the Study drug and is unexpected/unlisted based on the current TD-1473 Investigator's Brochure. In this case, all investigators will receive notification of the event. The investigator is responsible for notifying the Institutional Review Board or Ethics Committee and documenting the notification, as required by local regulatory authorities and in accordance with the local institutional policy.

7.5. Adverse Event Follow-up

A subject experiencing an AE or SAE or AESI will be followed by the investigator or his/her trained delegate(s) through the follow-up visit or until the investigator and/or the Sponsor has determined that the AE or SAE or AESI has resolved or a stable clinical endpoint is reached, whichever is longer. The Sponsor may request follow-up of certain adverse events until resolution and documentation of assessments made during this period.

The investigator must take all therapeutic measures necessary for resolution of an SAE or an AESI. Any medications necessary for treatment of the SAE or AESI must be recorded in the concomitant medication section of the case report form.

